4.1. Eligibility Criteria (Part A)

4.1.1. Eligibility Criteria for Transplant Recipients (Group A1, Group A2, and Group A3)

4.1.1.1. Inclusion Criteria for Transplant Recipients

Each participant must meet all of the following criteria at the screening visit (Day 0) or at Day 1, unless noted otherwise, to be enrolled in this study:

1. Is an adult male or female individual, at least 18 years of age at the time of signing informed consent (Day 0), is EITHER a kidney or liver (single organ) transplant recipient who is at least 90 days after transplantation at the time of consent, and is EITHER:
 - a. Unvaccinated, or
 - b. Previously vaccinated with 2 doses of Moderna COVID-19 vaccine who is at least 1 month after the second dose at the time of consent. Participants who received the 2 doses of Moderna COVID-19 vaccine before transplant are not eligible.
2. Received chronic immunosuppressive therapy for the prevention of allograft rejection for a minimum of 90 days before signing consent, including but not limited to: glucocorticoids (eg, prednisolone), immunophilin binding agents (eg, calcineurin inhibitors, mTOR inhibitors), or inhibitors of de novo nucleotide synthesis (eg, mycophenolic acid, mizoribine, leflunomide, azathioprine).
3. Understands, agrees, and is able to comply with the study procedures and provides written informed consent.
4. Female participants of childbearing potential may be enrolled in the study if the participant fulfills all the following criteria:
 - Has a negative pregnancy test at Screening and on the day of the first dose (Day 1)
 - Has practiced adequate contraception or has abstained from all activities that could result in pregnancy for at least 28 days prior to the first dose (Day 1)

- Has agreed to continue adequate contraception through 3 months following the second dose (Day 29) for those receiving 2-dose regimen, through 3 months following the third dose (Day 85) for those receiving 3-dose regimen, and through 3 months following the third dose (Day 1) for those previously vaccinated SOT recipients
- Is not currently breastfeeding

See [Section 10.3](#), Appendix 3 for Contraceptive Guidance.

5. Is medically stable, according to investigator's judgment, during the 3 months before signing consent. Medically stable is defined as having no significant worsening of a medical condition requiring medical intervention (eg, hospitalization, change in medical therapy).

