4.2. Study Eligibility Criteria (Part B)

4.2.1. Inclusion Criteria (Group B2, Group B3, Group B4, and Group B5)

1. a. Participants must have been previously enrolled in the mRNA-1273-P304 study, are actively participating in Part A and are at least 4 months from the last dose, or
b. Is an adult male or female individual, at least 18 years of age at the time of signing informed consent, is EITHER a kidney or a liver (single organ) transplant recipient who

is at least 90 days after transplantation at the time of consent AND who completed primary vaccination series (3 doses for mRNA COVID-19 vaccine; 2 doses for non-mRNA COVID-19 vaccine or at least 1 dose of non-mRNA combined with 1 dose of mRNA COVID-19 vaccine) under the EUA who are at least 4 months from the last dose. All primary COVID-19 vaccination series must be completed after transplant.

2. Female participants of childbearing potential may be enrolled in the study if the participant has a negative pregnancy test on the day of the booster dose injection (BD-Day 1).

4.2.2. Exclusion Criteria (for Participants who Completed Primary Vaccine Series under EUA) (Group B4)

Exclusion Criteria in Part A will apply except prior or planned administration of a coronavirus vaccine and current treatment with investigational agents for either prophylaxis against COVID 19.

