7.1.3. Safety Laboratory Assessments

All safety laboratory assessments will be conducted at laboratories local to the study sites. To help monitor for potential event of organ transplant rejection in the SOT recipients, safety laboratory assessments will be performed, including assessments related to kidney and liver function (eg, serum creatinine, urine protein, and UPCR for kidney SOT recipients; and ALT, AST, ALP, and bilirubin for liver SOT recipients) at prespecified study visits. After Day 57 (unvaccinated SOT recipients who receive 2 vaccine doses [Group A1]) or after Day 113 (unvaccinated SOT recipients who receive 3 vaccine doses [Group A2]) or after Day 29 (previously vaccinated SOT recipients who receive dose 3 [Group A3] in Part A or SOT recipients who completed the primary vaccination series who receive BD [Group B4]) in Part B, the investigator will review standard-of-care laboratory assessments related to kidney and liver function (as applicable), and report any laboratory-related AEs and suspected or confirmed events of organ transplant rejection until the EOS. The investigator must review results of safety laboratory assessments as soon as they are available. Schedules of sampling for safety laboratory assessments are presented in the SoEs- ([Section 10.1](#)).

A point-of-care urine pregnancy test will be performed at the screening visit (Day 0) and before each dose of vaccine. One pregnancy test is sufficient if Day 0 and Day 1 are combined in the same. At any time, a pregnancy test either via blood or point-of-care urine can be performed, at the discretion of the investigator. Pregnancy is one of the exclusion criteria ([Section 4.1.1.2](#) and [Section 4.1.2.2](#)) in this study and is a reason for dosing discontinuation ([Section 6.2](#)). Appendix 3 ([Section 10.3](#)) details the study guidance on contraception.

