18. Trained study site personnel will call all participants to collect information relating to any AEs, MAAEs, SAEs, AESIs, AEs leading to discontinuation from dosing and/or study participation (withdrawal), information on concomitant medications associated with those events, and any nonstudy vaccinations. In addition, study personnel will collect information on known participant close contact exposure to someone with known COVID-19 or SARS-CoV-2 infection and on participant experience of COVID-19 symptoms.
19. All concomitant medications and nonstudy vaccinations will be recorded through 28 days after each injection; all concomitant medications relevant to or for the treatment of an SAE, confirmed (biopsy-proven) or suspected events of organ transplant rejection, or MAAE will be recorded from Day 1 through the final visit (Day 394).
20. All immunosuppressant medications, for 3 months prior to Screening and throughout the study. Any change in the maintenance therapy should be recorded and the reason for the change documented.
21. Additional safety calls every 4 weeks should be scheduled if the last dose was delayed and there is a gap beyond 28 days between the safety call scheduled on D377 and the last study visit.

Table 8: Primary Schedule of Events for Unvaccinated Participants Who Receive the 3-Dose Vaccination Regimen (Part A: Group A2)

Visit Number	0	1	2	3	4	5	6	7	8	-	9	-	10		
Type of Visit	C	C	C	C	C	C	C	C	SFU		C	SFU		C	
Month Timepoint		M0		M1		M2	M3		M4	eDiary	SC	M9	eDiary	SC	M15
Study Visit Day	D0 ¹ (Screening)	D1 (Baseline)	D8 ²	D29 ³	D36 ^{2,3}	D57 ^{2,3}	D85 ^{2,3}	D92	D113 ^{2,3}	Every 4 weeks D127 – D239 ^{3,4}	Every 4 weeks D141 – D253 ^{3,5}	D265 ^{2,3}	Every 4 weeks D279 – D419 ^{3,4}	Every 4 weeks D293 – D433 ^{3,5}	D450 ^{2,3}
Window Allowance (Days)	-7		+3	-3/+7	+3	-3	-3/+7	+3	-3/+7	±2	±3	±14	±2	±3	±14
Days Since Most Recent Injection	-	0	7	28/0	7	28	56/0	7	28	-	-	180	-	-	365
Informed consent form, demographics, concomitant medications, medical history	X														
Review of inclusion and exclusion criteria	X	X													
Physical examination including height and weight ⁶	X	X		X		X	X		X			X		X	
Lymph node assessment ⁷		X	X	X	X		X	X							
Vital signs ⁸	X	X		X		X	X		X			X		X	
Pregnancy test ⁹	X	X		X		X									
Blood and urine sampling for safety assessments ¹⁰		X	X	X	X	X	X	X	X						
Recording of standard-of-care kidney or liver laboratory -related AEs ¹¹										X	X	X	X	X	X

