Study injection (including 30-minute post-dose observation period)		X		X			X								
Blood for immunogenicity and assessment of Ab against nonvaccine antigen ¹²		X		X		X	X		X			X		X	
Blood for cell-mediated immunity analysis ¹³		X			X			X							

Visit Number	0	1	2	3	4	5	6	7	8	-	9	-	10		
Type of Visit	C	C	C	C	C	C	C	C	SFU		C	SFU		C	
Month Timepoint		M0		M1		M2	M3		M4	eDiary	SC	M9	eDiary	SC	M15
Study Visit Day	D0 ¹ (Screening)	D1 (Baseline)	D8 ²	D29 ³	D36 ^{2,3}	D57 ^{2,3}	D85 ^{2,3}	D92	D113 ^{2,3}	Every 4 weeks D127 – D239 ^{3,4}	Every 4 weeks D141 – D253 ^{3,5}	D265 ^{2,3}	Every 4 weeks D279 – D419 ^{3,4}	Every 4 weeks D293 – D433 ^{3,5}	D450 ^{2,3}
Window Allowance (Days)	-7		+3	-3/+7	+3	-3	-3/+7	+3	-3/+7	±2	±3	±14	±2	±3	±14
Days Since Most Recent Injection	-	0	7	28/0	7	28	56/0	7	28	-	-	180	-	-	365
Nasopharyngeal swab sample for SARS-CoV-2 ¹⁴		X		X		X	X		X						
Surveillance for COVID-19/ Illness visit ^{15/} Unscheduled visit		X	X	X	X	X	X	X	X	X	X	X	X	X	X
Convalescent visit ¹⁶		X	X	X	X	X	X	X	X	X	X	X	X	X	X
eDiary activation for recording solicited ARs (7 days) ¹⁷		X		X			X								
Review of eDiary data			X		X			X							
Follow-up eDiary questionnaires										X			X		
Follow-up safety telephone calls ¹⁸											X			X	
Recording of unsolicited AEs		X	X	X	X	X	X	X	X						
Recording of MAAEs and concomitant medications relevant to or for the treatment of the MAAE ¹⁹		X	X	X	X	X	X	X	X	X	X	X	X	X	X
Recording of AESIs ¹⁸		X	X	X	X	X	X	X	X	X	X	X	X	X	X
Recording of SAEs and concomitant medications relevant to or for the treatment of the SAE ¹⁹		X	X	X	X	X	X	X	X	X	X	X	X	X	X
Recording of suspected AND confirmed organ transplant rejection ¹⁹		X	X	X	X	X	X	X	X	X	X	X	X	X	X

Visit Number	0	1	2	3	4	5	6	7	8	-	9	-	10		
Type of Visit	C	C	C	C	C	C	C	C	SFU		C	SFU		C	
Month Timepoint		M0		M1		M2	M3		M4	eDiary	SC	M9	eDiary	SC	M15
Study Visit Day	D0 ¹ (Screening)	D1 (Baseline)	D8 ²	D29 ³	D36 ^{2,3}	D57 ^{2,3}	D85 ^{2,3}	D92	D113 ^{2,3}	Every 4 weeks D127 – D239 ^{3,4}	Every 4 weeks D141 – D253 ^{3,5}	D265 ^{2,3}	Every 4 weeks D279 – D419 ^{3,4}	Every 4 weeks D293 – D433 ^{3,5}	D450 ^{2,3}
Window Allowance (Days)	-7		+3	-3/+7	+3	-3	-3/+7	+3	-3/+7	±2	±3	±14	±2	±3	±14
Days Since Most Recent Injection	-	0	7	28/0	7	28	56/0	7	28	-	-	180	-	-	365
Recording of concomitant medications and nonstudy vaccinations ¹⁹		X	X	X	X	X	X	X	X	X	X	X	X	X	X
Recording of concomitant immunosuppressant medications ²⁰	X	X	X	X	X	X	X	X	X	X	X	X	X	X	X
Study completion															X

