8. Vital signs are to be measured pre- and post-dose on days of injection (Day 1, Day 29, and Day 85). When applicable, vital signs should be measured before blood collection. Participants who are febrile (body temperature $\geq 38.0^{\circ}\text{C}/\geq 100.4^{\circ}\text{F}$) before injection on Day 1, Day 29, or Day 85 must have the visit rescheduled within the relevant visit window to receive the injection. Afebrile participants with minor illnesses can be enrolled at the discretion of the investigator.
9. The pregnancy test at Screening, Day 1, and before the second and third study injections will be a point-of-care urine test. At the discretion of the investigator, a pregnancy test either via blood or point-of-care urine test can be performed at any time.
10. Samples for safety laboratory assessments (serum creatinine, urine protein, and UPCR for kidney transplant recipients only; ALT, AST, ALP, and bilirubin for liver transplant recipients only) must be collected prior to dosing on Day 1, Day 29, and Day 85.
11. After Day 113, the investigator will review standard-of-care kidney and liver laboratory assessments and report any laboratory-related AEs and suspected or confirmed events of organ transplant rejection until the EOS.
12. Samples for immunogenicity (bAb against SARS-CoV-2 spike protein and neutralizing antibody against SARS-CoV-2) and assessment of SARS-CoV-2 bAb against the nonvaccine antigen (nucleocapsid protein) must be collected prior to dosing on Day 1, Day 29, and Day 85.
13. For assessment of cellular immune response, blood samples will be collected on Day 1 (prior to dosing), Day 36, and Day 92 from a subset of at least 50 unvaccinated SOT recipients (kidney or liver).
14. The NP swab sample will be collected prior to dosing and used to ascertain the presence of SARS-CoV-2 via RT-PCR.

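### Table 8 (three-dose regimen), as read from the PDF, marks a pregnancy test at Day 57, when no dose is given, and none at Day 85, the third dose, which does not agree with its own footnote 9, Section 7.1.3 or SAP 6.3.4

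*Protocol*

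**What the plan says.** The rule appears in three places. Protocol Section 7.1.3: "A point-of-care urine pregnancy test will be performed at the screening visit (Day 0) and before each dose of vaccine". Footnote 9, attached to the pregnancy-test row of Table 8 (Section 10.1, Group A2): "The pregnancy test at Screening, Day 1, and before the second and third study injections will be a point-of-care urine test". SAP Section 6.3.4 repeats the per-dose rule and extends it to the booster.

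The grid is Table 8 itself. Its pregnancy-test row carries four marks, "Pregnancy test ⁹ X X X X", which by column position fall at Day 0, Day 1, Day 29 and Day 57. The injection row carries three, "Study injection (including 30-minute post-dose observation period) X X X", at Day 1, Day 29 and Day 85. The timing row, "Days Since Most Recent Injection - 0 7 28/0 7 28 56/0 7 28", shows that Day 57 is 28 days after dose 2 with no dose that day, and that Day 85 is a dosing day, 56 days after dose 2.

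Two further provisions matter. Section 7 (general considerations) requires study procedures and their timing to follow Section 10.1 as it stands. Section 7.5.7 provides that a participant with a positive test during the study gets no further vaccine.

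**The concern.** The grid and its own footnote point to different visits. After Day 1, one marked visit (Day 57) has no dose and one dosing visit (Day 85) has no mark. Because Section 7 makes the schedule binding, the marks are operative text and not just a summary of the rule stated elsewhere.

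A positive result stops further dosing, so the timing of the test bears on whether dose 3 is given. Under Amendment 4, newly enrolled unvaccinated transplant recipients are to receive three doses in Part A, so Table 8 is their schedule. At stake is a participant of childbearing potential in Group A2 receiving dose 3 on an old result. No estimate or interval in the SAP depends on this; Section 6.3.4 plans only a listing for participants with positive tests.

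**Working it through.** The plan gives no figure to reproduce. The check has three parts.

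**1. Marks against doses in Table 8.** The table has 15 columns: D0, D1, D8, D29, D36, D57, D85, D92, D113, eDiary, safety call, D265, eDiary, safety call, D450.

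| Row | D0 | D1 | D29 | D57 | D85 |
|---|---|---|---|---|---|
| Pregnancy test | X | X | X | X | – |
| Study injection | – | X | X | – | X |
| Required by footnote 9 | X | X | X (before dose 2) | – | X (before dose 3) |

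The last line assigns each pre-dose test to its dosing visit. In Table 7, the two-dose grid, the pregnancy test is marked at D0, D1 and D29 and so agrees with its own dosing days.

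**2. Could the mark have moved when the PDF was read?** Ten other rows were compared with their footnotes or the text over D0 to D113: physical examination, lymph nodes, vital signs, safety laboratory samples, injection, immunogenicity, cell-mediated immunity, nasopharyngeal swab, eDiary activation and eDiary review. All ten fall on the right days in that range.

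At the far right, three of them (physical examination, vital signs, immunogenicity) show the D450 mark under the last safety-call column. Footnote 6 places an examination at D450, so this is a slip of one column. In those rows two consecutive blanks were read as one. A pregnancy row truly marked at D29 and D85 would also have two consecutive blanks (D36 and D57), and losing one would give exactly what is seen. The slipped rows still have 15 cells, so a full cell count does not rule this out.

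Against a slip, the injection and eDiary-activation rows have the same D36–D57 pair of blanks and kept both. The cell-mediated immunity and eDiary-review rows kept both blanks between D36 and D92. A slip is therefore unlikely but not excluded.

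**3. Age of the last marked test at dose 3.** Age = day of dose 3 − day of the last marked test. Inputs from Table 8: D57 window −3 days (54 to 57); D85 window −3/+7 days (82 to 92); footnote 3 allows D85 + 21 = D106 when the pandemic disrupts the visit.

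- Nominal: 85 − 57 = 28 days
- Shortest, standard windows: 82 − 57 = 25 days
- Longest, standard windows: 92 − 54 = 38 days
- Longest, extended window: 106 − 54 = 52 days

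These figures assume that the Day 57 test is done on site within its window, that windows are counted in study days as printed, and that no discretionary test is added.

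**The case against.** The strongest objection is that the point rests on the column of one mark in a table read from PDF, in which three rows are known to have slipped. That stands as a reason to look at the rendered page first. A reader might infer from the correctly placed neighbouring rows that a slip is ruled out. It is not, because the known slips are specific to a row.

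Second, the requirement is already stated on the row itself through footnote 9, and again in Section 7.1.3 and the SAP. This stands in part. A reader might infer that sites will dose without the test, or that every Group A2 woman of childbearing potential is affected. The documents do not support that, since it would require a site to ignore the footnote marker. The exposure is limited to sites that work from the marks alone. The objection does not remove the mismatch, because Section 7 directs sites to the schedule.

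Third, neither Section 7.1.3 nor footnote 9 says that the test must be on the day of dosing, so a Day 57 test is literally earlier than dose 3. That is true, but at Day 1 and Day 29 the grid puts the test on the dosing day. If a test four weeks earlier is meant to suffice for dose 3, no passage says so.

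Fourth, the Amendment 2 history might be read as proof of a leftover error. It records removal of a Day 57 pregnancy test from the two-dose table because no dose is given then, and removal of the Day 57 eDiary activation from the three-dose table. It lists no pregnancy-test change for the three-dose table. That fits a leftover mark, but also fits a mark that was never at Day 57. The log describes superseded text and settles neither.

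**Conclusion.** The point holds as a mismatch between the Table 8 marks, as read, and the testing rule in footnote 9, Section 7.1.3 and SAP 6.3.4. The possible consequence is a third dose given on a test nominally 28 days old, with a range of 25 to 38 days in the standard windows and up to 52 days with the extension. It concerns Group A2 participants of childbearing potential at sites that follow the marks and not the footnote; the documents give no number for them. The conclusion depends on the rendered table confirming the mark at Day 57. It is a small safety correction to operative text, with no effect on the analysis.

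A reader might extend the point to contraception, because Part A asks for a commitment ("Has agreed to continue adequate contraception through 3 months following the second dose (Day 29) for those receiving 2-dose regimen", with parallel wording for the other regimens), whereas the Part B criterion reads "Female participants of childbearing potential may be enrolled in the study if the participant has a negative pregnancy test on the day of" the booster injection. The documents do not support calling this a contradiction. The two criteria govern different parts of the study, the Part A wording is tied to Part A doses, and no passage carries it over to the booster. Group B4 never entered Part A at all.

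**What to change.** Look at the rendered Table 8 once. If the pregnancy-test mark is in the Day 85 column there, nothing needs to change. If it is in the Day 57 column, reconcile the row, and any visit map or data-entry form built from it, with footnote 9, Section 7.1.3 and SAP 6.3.4, so that all four state the same requirement for dose 3. Which timing is intended is for the sponsor to state; none is proposed here.

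The cost is one row of one table plus the matching visit map. Sample size, analysis sets and planned outputs are unchanged.
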